Official Study Title: Detecting Neonatal Hypoglycemia Using Real-Time Continuous Glucose Monitoring (CGM)

NCT Number: NCT03032523

Date of Document: 3/6/2019

PROTOCOL

TITLE

Detecting Neonatal Hypoglycemia using Real-Time Continuous Glucose Monitoring (CGM)

SUMMARY

Newborn infants have many complex physiological changes taking place that are difficult to anticipate. Infants born to mothers who have diabetes during their pregnancy are especially vulnerable to hypoglycemia. Our study will evaluate blood sugar changes during the first few days of life and the utility of CGM systems to detect clinically significant hypoglycemia in infants. This randomized, controlled single-blind trial will compare infants on CGM alone versus those using CGM who are remotely monitored by a physician through the Dexcom Share application. The number of hypoglycemic events that are detected in each group will be compared. For each time point that the unblinded CGM group has a low blood sugar level, it will be verified by standard heelstick (capillary) measures. Finally, the sensitivity and specificity of detecting hypoglycemia in the infant will also be determined.

INCLUSION CRITERIA

- Participants must be born at 34 weeks gestation or later
- Participants must be admitted Lucile Packard Children's Hospital
- Infants born at outside hospitals and transferred to LPCH will be eligible for the study
- Mothers have a diagnosis of pre-gestational diabetes
- Mothers with gestational diabetes have poorly controlled gestational diabetes defined as elevated Hemoglobin A1c (greater than 6%) during pregnancy or hyperglycemia based on home glucometer readings while pregnant. This includes fasting or pre-prandial blood glucose values of greater than 100 mg/dl, post-prandial blood glucose values greater than 140mg/dl at 1 hour or greater than 120mg/dl at 2 hours consistently.
- Any mothers who require insulin, metformin, or glucose lowering medications during gestation

EXCLUSION CRITERIA

- Infants <2,000g will be excluded from the study.
- If infants receive Acetaminophen, sensor readings will not be included in the analysis for 6 hours after the medication is given because this medication may falsely raise the sensor's glucose readings.
- Infants will also be excluded if they have an anomaly of the skin or subcutaneous tissue that would prevent proper adhesion, placement, and function of the sensor.
- If at any point in time the infant must undergo MRI, CT scan, or diathermy treatment, the sensor, receiver, and transmitter will be removed from the patient completely.

ENROLLMENT PROCEDURES:

- Flyers advertising the study will be posted at the obstetrics clinics at Stanford University.
- Parents of potential participants will be screened remotely for eligibility in the study.
- Every effort will be made to ensure eligible mothers of participants will be recruited and consented by study team members prior to delivery.
- Witnessed telephone consent may be obtained if the family is unable to meet in person.
- The general study, risks, and benefits will be discussed with all potential participants' legal guardians prior to enrollment

STARTING THE DEXCOM CGM: Application

- Participants enrolled in the study will be followed remotely to determine time of delivery of the infant (study participant).
- A trained study team member or staff member will contact the attending physician on call for the newborn to let them know that the participant is enrolled in the study.
- The trained study team member or staff member will come to the infant's bedside and place the Dexcom sensor according to the following steps.
- A Dexcom G4 CGM sensor (Dexcom, San Diego, CA) will be applied using the following steps.
 - After using Standard Precautions, a trained staff member will examine the skin for possible sensor sites.
 - An appropriate area of healthy, in-tact skin will be cleansed and allowed to dry. The sensor will be subcutaneously inserted by trained staff according to the Dexcom user's manual.
 - The transmitter will then be fastened on top of the sensor. The blinded receiver will be kept near the patient to ensure a proper signal as much as possible during the study period.
 - In the remote monitoring group, Dexcom receivers will be blinded to the clinical staff directly caring for the patient by blinding the device using Dexcom Studio. After blinding the receiver, it will be connected to an Ipad that will connect to the Stanford internet. Using the Dexcom Share application installed on the Ipad, the blinded receiver will send glucose data to the Ipad which will remain locked and inaccessible to clinical staff during the study period. The Dexcom Share application will send information to the study physician through the Dexcom Follow application on the study physician's encrypted phone to allow remote monitoring of patients in the experimental group.
 - Using the Dexcom Follow Application, auditory and vibratory alerts will be enabled for blood glucose values <46 mg/dl or signal loss for >60 minutes and sent directly to the study physician remotely monitoring participants.
 - Signal loss of greater than 3 hours will require participants to have a new subcutaneous sensor inserted and the initial calibration steps will need to be repeated.
- Dexcom Receivers and Ipods will remain connected to a power source as much as possible during the study period.

DEXCOM CGM PROTOCOL: Calibration

- After the initial 2 hour start-up period, the sensor will be calibrated using two successive capillary blood glucose measurements using a study glucometer.
- The same type of device will be used for all capillary blood glucose measurements performed on the infant.
- For each capillary blood glucose sample, an area of skin will be cleansed, allowed to dry, pricked using a sterile lancet, and the smallest amount of blood possible will be used for proper testing.
- Every effort will be made to ensure capillary blood glucose levels are checked at least every 12 hours from the time of initial calibration until the time of discharge or 7 days of life, whichever comes first.
- Glucose levels will be entered into the transmitter for calibration within 5 minutes of obtaining the glucose measurement.
- In the remote monitoring group, a trained study staff member will work with nursing staff to perform and input the calibration measurements into the receiver.

MONITORING FOR HYPOGLYCEMIA

- When the monitoring physician receives an alert for a low glucose value <46 mg/dl, they will contact the nurse taking care of the patient. First, the infant will be assessed to see if excess pressure is being placed on the sensor due to positioning. If so, the infant may be repositioned and monitored to see if the glucose values rise above 45mg/dl. If CGM glucose values remain low, a bedside glucose reading will be performed. This value will be recorded in the chart and by the monitoring physician in the study. Based on the standard of care blood glucose reading, the staff will take appropriate measures based on the standard of care (see appendix).
- If the hypoglycemia alarm continues for an additional 60 minutes, the nurse caring for the patient will be prompted to obtain an additional standard of care blood glucose measurement.

- If the measurement at 60 minutes shows that the patient has a BG >45mg/dl, the CGM may be re-calibrated (see below).
- In the case of severe hypoglycemia (BG <35mg/dl) found in both control and experimental groups during routine calibration procedures will require that the clinical staff caring for the patient be notified to ensure safety of the patient.
- For all blood glucose measurements that are >20% different from the Dexcom CGM values in the experimental group, a blood glucose test may be performed to re-calibrate the sensor prior to the 12 hours. Sensor re-calibration will only occur between glucose values of 40 mg/dl and 400 mg/dl based on manufacturer guidelines.

MONITORING FOR SENSOR SITES FOR INFECTION

- Sensor sites will be assessed at least once per 12 hour nursing shift and as needed during nursing cares for the duration of the study.
- Evidence of inflammation (redness, swelling, discharge) will be documented and discussed with the clinical care and research team.
- If the sensor site is thought to be infected, the sensor will be removed immediately and appropriate steps will be taken to treat the infection by the clinical team managing the patient.

RISKS ASSOCIATED WITH CGM USE

When the needle and sensor are inserted, the child should expect to experience a small amount of pain for a few seconds. After insertion, your child may or may not feel some tenderness or pain.

Pain, inflammation or redness, swelling, minor infection, and minor bleeding at the sensor insertion site are possible risks with your child's use of the study device. In extremely rare cases an infection might spread to other parts of the body. Significant or serious health risks with the investigational device are not anticipated.

Minor irritation may occur where the adhesive pad is placed. This will occur in most research participants and should clear up within hours to not more than a week after removal. The child may experience some itching in the area during the healing process, which is normal. The child may develop an allergic reaction to one or more parts of the sensor and transmitter. This is similar to allergies that occur due to medical tape or jewelry. Allergic reactions will usually be mild and require only a skin cream to make them better. Severe allergic reactions are rare. If the child has an allergic reaction, study staff should be notified.

On rare occasion, the sensor may cause skin injury and tissue trauma known as medical adhesive-related skin injury (MARS). If this happens, study staff should be notified as soon as possible.

There is a chance that the sensor or needle may break during use of the device. This is not expected to occur; but, if it does, the study staff should be contacted about what to do. They will see if the child has symptoms of infection or inflammation, swelling, redness, or pain at the insertion site. Treatment will be provided if needed. If a sensor breaks, it may be left under the skin indefinitely as long as no portion of the wire sensor fragment is visible above the skin and there are no symptoms of infection, redness, and/or swelling.

The radio waves that the transmitter puts out will not hurt the family or their child, nor will the child be aware of them.

EVALUATION AND TREATMENT OF HYPOGLYCEMIA

- Clinical signs of hypoglycemia will be monitored and documented.
- Hypoglycemic events will be treated using the existing treatment protocol (appendix) and will only be based upon glucometer values

CONTACTING DEXCOM

- Dexcom Technical Support information will be distributed to study personnel and contacted as needed. The contact information is as follows: [name] and [name].

DEXCOM CGM REMOVAL

- The CGM will remain in place for 7 days or until the patient is discharged.
- If it is thought that additional value would be gained from continuing use of the CGM for clinical care after 7 days, the CGM may be continued in an unblinded fashion, however the data collected will not be used for the purposes of the study.
- If the sensor should become dislodged at any time during the study period, it will be replaced using the same protocol. However, a new area of healthy skin will be chosen for sensor placement.
- At the end of the study time period, the sensor will be carefully removed by trained staff.
- Skin will be examined carefully and any changes to the skin associated with sensor use will be documented.

DATA ANALYSIS

Data collection

Maternal data, including mother's age, pregnancy history, type of diabetes, and treatment of diabetes during pregnancy were collected. Neonatal characteristics collected included sex, race, ethnicity, gestational age, birth weight, type of delivery, and other risk factors for hypoglycemia. Perinatal stressors were defined as an Apgar score <7, admission to NICU, or treatment of the infant beyond the usual suctioning and stimulating that routinely occurs after birth.¹⁴ Prematurity was defined as birth at <37 weeks gestation. Small for gestational age (SGA) infants weighed less than the 10th percentile for gestational age, whereas large for gestational age (LGA) infants weighed greater than the 90th percentile for gestational age.

Power calculation

Using an older retrospective CGM device in a similar cohort of at-risk infants, Harris found that using similar SOC intermittent heel-stick glucose monitoring, 32% of infants had glucose levels <47 mg/dL.¹⁵ We estimated that in our cohort, the SOC would find 32% of these high-risk infants with glucose levels <47 mg/dL. We estimated that with a sample size of 40, we should be able to detect a higher CGM rate of hypoglycemia of *57% (80% power, alpha = 0.05, one sided). However, because we were unable to recruit 40 infants during the time frame of the randomized trial, we modified the study design; instead, our goal was to determine if there was additional benefit of using CGM monitoring to detect hypoglycemia missed by SOC testing and to determine the false-positive rate of CGM alerts for hypoglycemia.

Outcome measures

Hypoglycemia was defined as a glucose concentration of <45mg/dL in order to correspond with the hospital's SOC protocol. Primary outcome measures were the number of hypoglycemic events detected by the sensor that were not detected by the hospital SOC. Secondary outcome measures were sensitivity, specificity, and positive predictive value of the device to detect hypoglycemia. When evaluating number of hypoglycemic episodes that occurred with each infant, the start of each hypoglycemic episode needed to be at least 60 minutes from the last episode to allow for treatment and resolution of hypoglycemia. A duration of 60 minutes was used to allow time for breast feeding in accordance with the nursery's SOC procedures (Supplementary Fig. S1). The CGM data were reviewed post hoc using Dexcom Studio Software. Using the Dexcom Studio Software to calculate the average CGM glucose level for each infant, a value of 39 mg/dL was used for all values that were reported as "low." All values reported by the CGM as "low" were excluded from the accuracy analysis. The mean absolute relative difference (MARD) was calculated by taking the absolute value of the difference between the CGM and hospital glucometer values and dividing by the hospital glucometer value individually, and then taking the mean of these values.

Additional outcome measures included CGM feasibility in the hospital setting. During the recruitment process and throughout the study, we asked caregivers for feedback about satisfaction with the CGM device. If any devices were removed before the end of the study period, we requested feedback from the families as well.

DATA COLLECTION SCHEDULE

Measurement	Study Entry	Daily	End of Study
Demographics	X		
Medical History (mother)	X		X
Medical History (infant)	X		X
Chart Review		X	X
Adverse Events		X	X
Nutrition		X	X
Glycemic Trends		X	X
Exam of skin site/sensor site	X	X	X

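### In the remote group the sensor alert itself prompts a heelstick called standard of care, so the count of events missed by standard of care needs a counting rule and reporting by group

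*Combined protocol and SAP*

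**What the plan says.** **Design.** The SUMMARY states: "This randomized, controlled single-blind trial will compare infants on CGM alone versus those using CGM who are remotely monitored" by a physician. It does not say who is blinded. It then refers to the remote group as unblinded and promises confirmation of its lows: "For each time point that the unblinded CGM group has a low blood sugar level, it will be verified by standard heelstick (capillary) measures".

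**Masking.** For the remote group, the section on starting the CGM (Application) says: "Dexcom receivers will be blinded to the clinical staff directly caring for the patient by blinding the device using Dexcom Studio". The thing masked is the sensor display.

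**Alert pathway.** Under MONITORING FOR HYPOGLYCEMIA, when the study physician receives a low alert, "they will contact the nurse taking care of the patient". After a check for pressure on the sensor, "If CGM glucose values remain low, a bedside glucose reading will be performed". That reading goes into the chart, is termed a standard of care reading, and guides what staff do next. If the alarm lasts a further 60 minutes, the nurse is prompted for another reading, also termed standard of care.

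**Primary outcome.** Outcome measures counts sensor-detected events that the hospital SOC did not detect. No group is named, and prompted readings are not mentioned. Power calculation explains that 40 infants could not be recruited, so the aim became to find hypoglycemia missed by SOC and to estimate the false-positive rate of alerts.

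**The concern.** The primary outcome compares two detectors, the sensor and SOC. For that comparison to show what SOC misses, SOC must run as it would without the sensor. In the remote group it does not: the sensor decides when an extra heelstick is taken, and care follows from the result.

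The outcome definition leaves two things open: which infants contribute, and whether a prompted heelstick is an SOC detection. The second choice can decide even the direction of the bias. Someone analysing the data could take either route, in good faith, and reach quite different answers on the trial's main question.

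**Working it through.** The plan gives no figure for the share of events missed by SOC, so there is nothing to reproduce. The figures in the power calculation do not bear on this point. What follows puts the sections side by side and then illustrates each counting rule on stated assumptions.

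**Step 1. Is SOC independent of the sensor?** In the remote group, no. The chain under MONITORING FOR HYPOGLYCEMIA is alert, nurse contact, heelstick if the sensor stays low, chart entry, action. No such chain is described for CGM-alone infants.

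**Step 2. Prompted readings count as SOC.** Let *f* be the remote group's share of the events that routine SOC would have missed, and *c* the share of those caught by a prompted heelstick. Then

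reported missed count / true missed count = 1 − *f* × *c*

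Neither value is in the documents. Assume *f* = 0.5:

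| *c* | 1 − 0.5*c* |
|---|---|
| 25% | 87.5% |
| 50% | 75% |
| 75% | 62.5% |
| 100% | 50% |

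Misses are undercounted. The events still counted as missed in the remote group are then those where the prompted reading was not low or was not taken.

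**Step 3. Prompted readings do not count as SOC.** A low of length *L* hours is missed by routine tests every *T* hours with probability 1 − *L/T*, if test times are unrelated to the low. Suppose the response to an alert ends the low at *D* hours instead. The probability becomes 1 − *D/T*. The SOC interval is not in the supplied text, where only the appendix title appears, so *T* = 3 to 6 h and *L* = 1 to 2 h are assumptions. *D* = 0.5 h is also assumed. *D* = 1 h matches the 60 minutes that Outcome measures allows for treatment and resolution.

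| *T*, *L* | Undisturbed | *D* = 0.5 h | *D* = 1 h |
|---|---|---|---|
| 3 h, 1 h | 67% | 83% (+17 points) | 67% (0) |
| 3 h, 2 h | 33% | 83% (+50) | 67% (+33) |
| 6 h, 1 h | 83% | 92% (+8) | 83% (0) |
| 6 h, 2 h | 67% | 92% (+25) | 83% (+17) |

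These shifts apply within the remote group, and only if every low there is alerted and cut short. The overcount is 8 to 50 points with a 30-minute ending and 0 to 33 points with a 60-minute ending.

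**Step 4. Is CGM-alone pure SOC?** Not quite. Calibration heelsticks at least every 12 hours are not limited to one group. The section on monitoring for hypoglycemia also requires clinical staff to be told of calibration readings below 35 mg/dl in both groups.

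**The case against.** The strongest reply is that alerting the nurse is the intervention, so it is no flaw that SOC changes in the remote group. That is right for a comparison between groups. It does not help an outcome defined as what SOC misses.

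Several stronger readings are tempting, and the documents do not support them:

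- **That the plan pools the groups.** It never says so. The SUMMARY still describes a comparison, and Power calculation says only that the design was modified. The outcome merely names no group.
- **That the single-blind label is false.** It is unclear. The masked party is not named, and no section claims that the assignment is hidden. Nurses can infer the group when contacted about an alert. The iPad ("it will be connected to an Ipad that will connect to the Stanford internet") and the shared calibration work ("a trained study staff member will work with nursing staff to perform and input the calibration measurements into the receiver") are possible further cues, described only for the remote group.
- **That staff act on the assignment.** They act on alerts and the readings that follow. The section on evaluation and treatment of hypoglycemia ties treatment to glucometer values only.
- **That misses are overstated by a known amount.** The range depends on assumed inputs. The direction reverses if prompted readings count as SOC, which is what the wording of the alert pathway suggests.

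One objection to the remedy stands. Prompted verification is described only for the remote group, so a main estimate from CGM-alone infants may include false sensor lows.

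**Conclusion.** The point holds as a gap in the definition of the primary outcome. SOC in the remote group is not independent of the sensor, so that group cannot show what SOC alone misses, and a count that includes it is biased. If prompted readings count as SOC, the count falls to 50–87.5% of its true value under the assumptions in step 2. If they do not, it can be too high, because treatment may end a low before the next routine test. The documents fix neither the direction nor the size; the figures show only that either could be material. A reader might infer that the CGM-alone group shows undisturbed SOC. It is cleaner, but step 4 shows that it is not pure.

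**What to change.** 1. Classify every heelstick from the chart and study records as routine, calibration or alert-prompted.
2. Define SOC detection on routine tests only.
3. Report the missed count by group and do not pool it. The routine-only rule does not by itself remove the effect of treatment in step 3, so make CGM-alone the main estimate, show the remote group separately, and use the remote group for the false-positive rate of alerts.
4. Tabulate heelsticks per infant-day by group and type, as a check for changed testing.
5. State that CGM values, not the assignment, are masked from bedside staff. This changes no result but removes the ambiguity.

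**Cost.** Wording, chart classification and precision. The main estimate rests on fewer infants: if 40 were the total and allocation were 1:1 (neither is stated), about 40 / 2 = 20, and fewer because 40 was not reached. CGM-alone lows lack prompted verification, so report them beside the remote group's false-positive rate. State also that calibration heelsticks and the notification below 35 mg/dl apply in that group. Changing who performs calibration is not proposed, because the data analysis section already describes recruitment and data collection in the past tense.

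### The 6-hour acetaminophen exclusion does not cover calibrations entered inside the window, so readings kept after it can be falsely low and can count as hypoglycemia missed by standard of care

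*Combined protocol and SAP*

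**What the plan says.** All references are to the combined protocol and SAP.

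- **EXCLUSION CRITERIA.** The rule after acetaminophen is that "sensor readings will not be included in the analysis for 6 hours after the medication is given because this medication may falsely raise" what the device shows. This restricts the analysis only; it says nothing about calibration.
- **DEXCOM CGM PROTOCOL: Calibration.** Capillary glucose is to be "checked at least every 12 hours from the time of initial calibration", and "Glucose levels will be entered into the transmitter for calibration within 5 minutes of obtaining the glucose measurement". Neither statement has an exception for a recent dose.
- **MONITORING FOR HYPOGLYCEMIA.** An earlier calibration is allowed on disagreement. The trigger is worded "For all blood glucose measurements that are >20% different from the Dexcom CGM values in the experimental group", so it applies to one group only. The action it permits is optional: "a blood glucose test may be performed to re-calibrate the sensor prior to the 12 hours". The one limit given is on the glucose range: "Sensor re-calibration will only occur between glucose values of 40 mg/dl and 400 mg/dl".
- **Outcome measures.** "Hypoglycemia was defined as a glucose concentration of <45mg/dL". The primary outcome is the number of sensor-detected events that hospital SOC testing did not find. A blood value confirming the event is not part of the definition. Episodes must start at least 60 minutes apart.

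No section drops later readings that depend on a calibration made inside the 6-hour window.

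**The concern.** The exclusion rule treats the drug as a problem that ends at 6 hours. A calibration carries it further. If the sensor reads too high and is then matched to a true capillary value, the device may correct itself downward. Once the drug has cleared, that correction remains and the readings are too low until the next calibration. Those hours lie outside the exclusion and are kept, with the error reversed in sign.

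The direction matters for the primary outcome. SOC testing of a baby who is not hypoglycemic finds nothing, so a false sensor low fits the definition of a missed event. An error of this kind can only add to the apparent benefit of CGM. The same readings can lower specificity and positive predictive value and, where a numeric value is shown, worsen the MARD.

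**Working it through.** The plan gives no figure on this point to reproduce. The check is interval arithmetic on its own times, plus a simple calibration model that is an assumption.

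**Inputs from the documents.** Exclusion window 6 h (EXCLUSION CRITERIA); longest calibration interval 12 h (Calibration); hypoglycemia threshold 45 mg/dL and episode spacing 60 min (Outcome measures); discordance trigger 20% (MONITORING FOR HYPOGLYCEMIA).

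**Inputs not in the documents.** How many infants received acetaminophen, how far it raises the sensor, how long the interference lasts within the 6 h, and how the device uses a calibration value.

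**Step 1: chance that a calibration falls in the window.** One dose, calibration strictly every 12 h, timing unrelated to the dose: 6/12 = 50%.

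**Step 2: retained readings that depend on it.** Calibration at hour U after the dose (0 to 6); the next is at U + 12; time beyond the window is U + 12 − 6 = U + 6. The range is 6 to 12 h, with mean 9 h if U is uniform.

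**Step 3: how far Step 2 is an upper-range figure.**
- It gives full interference to every hour of the window. If interference instead falls linearly to zero at 6 h (assumption), weight each tail by 1 − U/6. The mean of (U + 6)(1 − U/6) over 0 to 6 is (1/6) × ∫(6 − U²/6)dU = (36 − 12)/6 = 4 full-effect hours, not 9.
- Twelve hours is the longest scheduled interval. At 8-hourly, the probability is 6/8 = 75% and the tail U + 2 (mean 5 h). At 6-hourly, the probability is 100% and the tail U (mean 3 h). Probability times mean tail per dose is 4.5, 3.75 and 3 h for 12-, 8- and 6-hourly calibration: smaller, but not zero.

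**Step 4: size of the error.** Single-gain model (assumption): a sensor inflated by a factor 1 + b when calibrated later reads G/(1 + b) at true glucose G. It reads below 45 when G < 45(1 + b).

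| Inflation b at calibration (assumed) | Later bias, 1/(1 + b) − 1 | True glucose that reads <45 mg/dL |
|---|---|---|
| 10% | −9.1% | below 49.5 |
| 20% | −16.7% | below 54.0 |
| 30% | −23.1% | below 58.5 |
| 50% | −33.3% | below 67.5 |

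Conversely, the inflation needed is b > G/45 − 1: 11% at a true 50, 22% at 55, 33% at 60 and 56% at 70 mg/dL.

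**Step 5: link to the 20% rule.** Inflation just above 20%, measured against the glucometer, is enough to permit early re-calibration in the experimental group. At that inflation, true values up to about 54 would later read as hypoglycemia.

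**Step 6: ceiling on the count.** With 60-minute spacing, a 6 to 12 h tail has room for roughly 6 to 12 episodes per dose. This is a bound, not an estimate.

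**The case against.** **Possible, not shown.** A reader might infer that falsely low readings are in the data and inflate the primary count, or that each affected dose adds about 9 h of bad readings. The documents support neither. A spurious event needs an exposed infant, a calibration entered during interference, a device that rescales downward, true glucose near the threshold and no correction in between. The plan gives no exposure, no inflation size and no calibration algorithm; it defers to the manufacturer's material. The affected subgroup could be empty. All of this stands.

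**The remote group has checks.** An alert below 46 mg/dl that persists leads to a bedside glucose. A continuing alarm prompts another at 60 minutes, and a value above 45 mg/dl permits re-calibration. The 20% rule can also correct the error it helped to create. These steps can expose or shorten a false low there, and the false-positive rate of alerts is a stated aim. But re-calibration is optional, and biases of −9.1% and −16.7% do not reach 20% of the glucometer value. No text removes an event from the primary count after a normal bedside result. No equivalent alert-driven check is described for the blinded control group.

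**MARD.** Readings that the device reports only as low are left out of the accuracy analysis, so the most extreme false lows cannot worsen MARD. This stands; only numeric readings can affect it.

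**The general issue.** Sensor lows without blood confirmation are a wider weakness, and the protocol itself names pressure on the sensor as another cause. True, but here the plan already has a rule for the interference, and that rule stops short of its own premise.

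**Barring calibration in the window.** This would collide with the 12-hour schedule, leave repeated doses unaddressed and come too late: the Power calculation section reports that recruitment fell short of 40 during the randomized trial's time frame. That objection is sound, and the fix below does not rely on such a bar.

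**Conclusion.** The gap is real. The acetaminophen rule does not reach readings that depend on a calibration entered inside its own window. In an exposed infant such readings can be falsely low and, if unconfirmed, can count as hypoglycemia missed by SOC, most directly in the control group. Any error in the primary count runs toward CGM benefit.

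The 50% probability and the 6 to 12 h tail rest on a single dose, strict 12-hourly calibration and timing unrelated to the dose. The tail is at the upper end of what is plausible. The glucose limits rest on the single-gain model and on assumed inflation of 10 to 50%. The change in the event count cannot be computed from the documents, and nothing here shows that the result is wrong. The point merits correction because the remedy is specific and nearly free, not because the harm has been demonstrated.

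**What to change.** Add one rule to the data analysis section. Where any calibration was entered within 6 h after an acetaminophen dose, extend the exclusion until the first calibration entered more than 6 h after the last dose. Apply it to the event count, sensitivity, specificity, positive predictive value and MARD. Wording it by the last dose also covers repeated doses. Report the primary count with and without the extension, with the number of exposed infants and the sensor hours removed.

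The existing 6-hour rule already needs dose times. The extension also needs calibration times, which should be taken from the study records. It works on data already collected.

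The cost is a few more excluded sensor hours in exposed infants: on a strict 12-hourly schedule, 6 to 12 h after the window for a single dose, and fewer if calibration was more frequent. For any future use of the protocol, the calibration section and the acetaminophen rule must be reconciled.
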